17.1 Sample size calculation

The primary objective of this trial is to compare long-term glycaemic control of IDegLira vs. IGlar in insulin naïve subjects with T2DM inadequately controlled with OAD(s). This is established by comparing the time from randomization to the need for treatment intensification for IDegLira and IGlar using a stratified log-rank test.

Formally, let D be the hazard ratio for time to treatment intensification. The null-hypothesis of no treatment difference will be tested against the alternative hypothesis as given by

H₀: D = 1 against H_A: D ≠ 1

The need for treatment intensification is determined as the HbA_{1c} ≥ 7% at 2 consecutive visits from week 26 (including week 26, if HbA_{1c} was ≥ 7% at week 12). Subjects withdrawing from the trial or discontinuing treatment will contribute to the primary analysis as needing rescue therapy from the time of withdrawal/discontinuation. The data will inherently be interval censored, since HbA_{1c} is only measured at the scheduled visits while subjects may reach an HbA_{1c} ≥ 7.0% at any time between 2 visits.

The sample size is based on time from randomisation to the need of treatment intensification, a 1:1 randomisation scheme, a 5% significance level and exponential survival.

Based on experience from the phase 3a development program for IDegLira and IDeg, it is assumed that around 45% in the IDegLira arm will need treatment intensification compared with around 55% in the IGlar arm during the 2-year treatment period. Subjects withdrawing from the trial or discontinuing treatment are included in these proportions as needing treatment intensification. [Table 17-1](#) shows power calculations for varying effect sizes.

Table 17-1 Power for varying treatment differences

Percentage of subjects needing treatment intensification before end of trial	IDegLira: 40% IGlar: 55% HR: 0.65	IDegLira: 45% IGlar: 55% HR: 0.75	IDegLira: 50% IGlar: 55% HR: 0.86	IDegLira: 55% IGlar: 65% HR: 0.72
800 subjects	99%	83%	31%	85%
1000 subjects	>99%	90%	37%	92%

HR: hazard ratio

From these assumptions the sample size is set to 500 subjects per treatment arm; in total 1000 subjects will be randomised. This will provide 90% power to detect a hazard ratio of 0.75 for IDegLira relative to IGlar (i.e., a 25% reduction in the risk of needing treatment intensification) using a two group log-rank test and a two-sided significance level of $\alpha = 0.05$.

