17.3 Primary endpoint

The following endpoint will be assessed up to 104 weeks. Time from randomisation to inadequate glycaemic control and need for treatment intensification defined as an $\text{HbA}_{1c} \geq 7\%$ at 2 consecutive visits from week 26 (including week 26, if HbA_{1c} was \geq to 7% at week 12).

Subjects withdrawing from the trial or discontinuing treatment will contribute to the primary analysis as needing rescue therapy from the time of withdrawal/discontinuation. The data will inherently be interval censored, since HbA_{1c} is only measured at the scheduled visits while subjects may reach an $\text{HbA}_{1c} \geq 7.0\%$ at any time between 2 visits (including week 26 if HbA_{1c} was $>$ to 7% at week 12).

The primary endpoint will be analysed using a stratified log-rank test where treatment, baseline HbA_{1c} group and previous OAD treatment will be included as strata in the model.

The variable “baseline HbA_{1c} group” is a dichotomised baseline HbA_{1c} variable with 2 categories: $\text{HbA}_{1c} < 8.5\%$ or $\text{HbA}_{1c} \geq 8.5\%$.

The variable “previous OAD treatment” is a categorical variable with 2 categories: OAD(s) + sulphonylurea or OAD(s).

Formally, let D be the hazard ratio for time to treatment intensification. The null-hypothesis of no treatment difference will be tested against the alternative hypothesis as given by

$H_0: D = 1$ against $H_A: D \neq 1$

Kaplan-Meier curves by treatment arm and strata from the model will be presented.

Sensitivity analysis

The following two sensitivity analysis will be carried out.

The first sensitivity analysis will take the interval censored nature of the data into account by using a semi-parametric proportional hazards regression model for interval censored data. The chosen model can be viewed as an extension of Turnbull’s method²⁴ from a non-parametric model to a semi-parametric proportional hazards models as described in Alioum.²⁵

The log-likelihood function of the data under the proportional hazards assumption can be expressed as:

$\sum_{i=1, \dots, n} \log \left(\sum_{j=1, \dots, m} \mu_{ij} (S(p_{j-1})^{\exp(\beta zi)} - S(p_j)^{\exp(\beta zi)}) \right),$
where:

- μ_{ij} is 1 if subject i's observed interval encompass the j^{th} Turnbull interval and 0 if this is not the case
- p_j is the right endpoint of the j^{th} Turnbull interval
- z_i is the covariate vector for subject i and β is the corresponding vector of regression coefficients

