17.4 Secondary endpoints

17.4.1 Supportive secondary endpoints

17.4.1.1 Efficacy endpoints

Time from randomisation to HbA_{1c} > 6.5% at 2 consecutive visits from week 26.

Time from randomisation to HbA_{1c} > 6.5% at 2 consecutive visits from week 26 (including week 26 if HbA_{1c} was ≥ 6.5% at week 12).will be analysed and presented in the same way as the primary endpoint.

HbA_{1c}

Change from baseline in HbA_{1c} after 26 weeks of treatment will be analysed using the standard MMRM model.

Body weight

Change from baseline in body weight after 26 and 104 weeks of treatment will be analysed using the standard MMRM model.

Insulin dose after 26 and 104 weeks of treatment

The actual insulin dose will be summarised descriptively according to regimen as dose in units, and units/kg. The actual daily insulin dose will be analysed using the standard MMRM model.

HbA_{1c} responder after 26 and 104 weeks of treatment (yes/no)

Two dichotomous endpoints (responder/non-responder) will be defined based on whether a subject has met a specific target level after 26 and 104 weeks of treatment:

- HbA_{1c} target < 7.0%⁷
- HbA_{1c} target ≤ 6.5%²⁷

Analysis of each of the four responder endpoints will be based on a logistic regression model with treatment, HbA_{1c} group, previous OAD treatment and region as fixed factors and baseline HbA_{1c} value as a covariate. Subjects withdrawing from the trial or discontinuing treatment will be imputed as being non-responder from time of withdrawal/discontinuation in line with the evaluation of the primary endpoint.

HbA_{1c} responder endpoints without weight gain

Responder for HbA_{1c} without weight gain after 26 and 104 weeks of treatment will be defined as HbA_{1c} < 7.0% or ≤ 6.5% and change in body weight from baseline ≤ 0. Analysis of each of the 2 responder endpoints will be based on a logistic regression model with treatment, HbA_{1c} group, previous OAD treatment and region as fixed factors and baseline HbA_{1c} and baseline body weight as covariates. Subjects withdrawing from the trial or discontinuing treatment will be imputed as being non-responder from time of withdrawal/discontinuation in line with the evaluation of the primary endpoint.

HbA_{1c} responder endpoints without treatment-emergent severe or BG confirmed symptomatic hypoglycaemic episodes

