18.5 Premature termination of the trial and/or trial site

Novo Nordisk, the IRBs/IECs or a regulatory authority may decide to stop the trial, part of the trial or a trial site at any time, but agreement on procedures to be followed must be obtained.

If a trial is suspended or prematurely terminated, the investigator must inform the subjects promptly and ensure appropriate therapy and follow-up. The investigator and/or Novo Nordisk must also promptly inform the regulatory authorities and IRBs/IECs and provide a detailed written explanation.

If, after the termination of the trial, the benefit-risk analysis changes, the new evaluation must be provided to the IRBs/IECs in case it has an impact on the planned follow-up of subjects who have participated in the trial. If it has an impact, the actions needed to inform and protect the subjects should be described.

19 Protocol compliance

Deviations from the protocol should be avoided.

If deviations do occur, the investigator must inform the monitor and the implications of the deviation must be reviewed and discussed.

Deviations must be documented and explained in a protocol deviation by stating the reason, date, and the action(s) taken. Some deviations, for which corrections are not possible, can be acknowledged and confirmed via edit checks in the eCRF or via listings from the clinical database.

Documentation on protocol deviations must be kept in the investigator's trial master file and sponsor trial master file.

20 Audits and inspections

Any aspect of the clinical trial may be subject to audits conducted by Novo Nordisk or inspections from domestic or foreign regulatory authorities or from IRBs/IECs. Audits and inspections may take place during or after the trial. The investigator and the site staff as well as Novo Nordisk staff have an obligation to cooperate and assist in audits and inspections. This includes giving auditors and inspectors direct access to all source documents and other documents at the trial site relevant to the clinical trial. This includes permission to examine, analyse, verify and reproduce any record(s) and report(s) that are relevant to the evaluation of the trial.

21 Critical documents

Before a trial site is allowed to start screening subjects, the following documents must be available to Novo Nordisk:

- Regulatory approval and/or acknowledgement of notification as required

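### The primary analysis scores every treatment discontinuation as a failure, so an administrative site closure under 18.5 would turn well-controlled subjects into events and dilute the hazard ratio

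*Protocol*

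**What the plan says.** Section 18.5 allows for a stop imposed from outside: the sponsor, an ethics committee or a regulator "may decide to stop the trial, part of the trial or a trial site at any time". Its next paragraph also covers suspension: "If a trial is suspended or prematurely terminated, the investigator must inform the subjects promptly". The section requires that procedures be agreed but says nothing about the analysis.

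The event rule is in 17.3: "Subjects withdrawing from the trial or discontinuing treatment will contribute to the primary analysis as needing rescue therapy from the time of withdrawal/discontinuation". The same rule stands in the opening text of section 17 and in 17.1. None of the three places exempts any reason. For the responder endpoints, 17.4.1.1 says that such subjects "will be imputed as being non-responder from time of withdrawal/discontinuation".

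The sample size in 17.1 assumes that "around 45% in the IDegLira arm will need treatment intensification compared with around 55% in the IGlar arm during the 2-year treatment period", and adds that "Subjects withdrawing from the trial or discontinuing treatment are included in these proportions as needing treatment intensification". It is based on "a 1:1 randomisation scheme, a 5% significance level and exponential survival". The conclusion for 500 subjects per arm is: "This will provide 90% power to detect a hazard ratio of 0.75 for IDegLira relative to IGlar".

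**The concern.** The endpoint is meant to capture loss of glycaemic control and the need for intensified treatment. Counting intolerance, withdrawal of consent or lack of effect as failure is a defensible composite, and this point leaves it alone. An administrative closure is different, because it carries no information about the subject. A subject with HbA1c below 7% would be recorded as needing rescue therapy on the closure date.

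Closing a site removes both arms at the same moment. Let the event hazards be h1 (IDegLira) and h2 (IGlar), and let closure add a common hazard c. The ratio then changes from h1/h2 to (h1 + c)/(h2 + c), which is nearer 1 whenever h1 < h2. The estimated effect shrinks, both failure curves rise, and power can fall even though there are more events. As specified, neither interval-censored sensitivity analysis in 17.3 would show this, because neither handles discontinuations differently.

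**Working it through.** **Inputs from the protocol.** 500 subjects per arm, 45% v 55% events over 104 weeks, exponential survival, two-sided 5% log-rank test (17.1); recruitment over 32 weeks (section 7).

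**Inputs assumed.** The share of subjects at closed sites and the closure time. The protocol gives neither.

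**Step 1: the plan's own figure.**
- Hazards per week: h1 = -ln(0.55)/104 = 0.00575; h2 = -ln(0.45)/104 = 0.00768.
- HR = 0.00575/0.00768 = 0.749; ln HR = -0.2894.
- Expected events D = 500 × 0.45 + 500 × 0.55 = 500.
- Power = Φ(√D/2 × |ln HR| - 1.96) = Φ(11.18 × 0.2894 - 1.96) = Φ(1.28) = 89.9%.

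The stated 90% reproduces.

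**Step 2: event counts under the rule as written.** If a share q of subjects is at closed sites, all of them become events by the closure date at the latest. The expected count per arm is 500(1 - q)p + 500q, where p is 0.45 or 0.55.

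| q | IDegLira | IGlar | Total |
|---|---|---|---|
| 2% | 490 × 0.45 + 10 = 230.5 | 490 × 0.55 + 10 = 279.5 | 510 |
| 5% | 475 × 0.45 + 25 = 238.75 | 475 × 0.55 + 25 = 286.25 | 525 |
| 10% | 450 × 0.45 + 50 = 252.5 | 450 × 0.55 + 50 = 297.5 | 550 |

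At 10% the failure percentages rise from 45% and 55% to 50.5% and 59.5%.

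**Step 3: hazard ratio and power by simulation.** Exponential times at h1 and h2, uniform entry over 32 weeks, 104 weeks of follow-up, unstratified log-rank test, closure 68 weeks after the first entry, 8000 runs per row. The simulation error of a power near 90% is √(0.9 × 0.1/8000) = 0.3 points.

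| Share closed | As written: HR, events, power | Censored at closure: HR, events, power |
|---|---|---|
| 2% | 0.755, 510, 88.8% | 0.749, 496, 89.6% |
| 5% | 0.763, 525, 87.2% | 0.748, 490, 89.6% |
| 10% | 0.777, 550, 84.6% | 0.749, 479, 89.3% |

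At 10% the rule as written has 71 more events (550 - 479) and still has less power.

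**Step 4: cross-checks.**
- The Step 1 formula with the as-written hazard ratios and event counts gives 88.8%, 87.3% and 84.1%. With the censored values it gives 89.6%, 89.5% and 88.5%. The losses are therefore about 1, 2 and 4 to 5 points.
- With event times rounded up to a 13-week grid, the 10% case gives 84.0% v 88.0%.
- Closure at week 52 of a group of 9% gives 83.3% v 88.0%. Nine per cent is the size of the 90 subjects planned for Mexico in 6.1.
- With no true difference and 10% closed, the rejection rate as written is 4.7%, so type I error is not inflated.

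**The case against.** **This belongs in the SAP.** Censoring details for rare administrative stops usually do. Here, however, the protocol states the event rule without exception, so an SAP that censored closures would be changing the rule, not filling a gap.

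**The literal reading is not forced.** Section 6.4 lists subject-level reasons, 8.1.8 ties its procedures to those criteria, 6.5 defines withdrawal by the subject's refusal of further contact, and 18.5 uses other words for a stop. This has some weight: the text can be read either way. But 17.3 is not limited to the reasons in 6.4, and the choice should be made before any closure happens.

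**There are safeguards already.** The agreement on procedures in 18.5 does not concern the analysis. The data review in 17.2 would be a case-by-case decision in an open-label trial, and excluding randomised subjects sits badly with the intention-to-treat principle stated there.

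**The loss may be counted twice.** The 45% and 55% already include discontinuations, while the simulation adds closures on top. The protocol does not say whether any closures informed those figures. If they did, the stated power already allows for them, but the estimated hazard ratio would still be diluted.

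**Stronger readings that the documents do not support.** A reader might infer that the promised 90% power is not delivered. It is delivered under its stated assumptions; no closure is planned, and one small site costs little. A reader might also take a whole-trial stop as the measure of the problem: stopped at week 80 after first entry, power is 35% as written v 75% with censoring. That is an extreme case, in which the 104-week analysis would hardly be run unchanged. Finally, a reader might want every stop under 18.5 censored. A stop of one arm, or a stop for product safety or efficacy, is related to treatment; censoring there would be informative and could favour the stopped product.

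**Conclusion.** The point holds in a limited form. The rule in 17, 17.1 and 17.3, applied as written, turns controlled subjects at administratively closed sites into primary events and moves the hazard ratio towards 1. Measured against censoring at closure, the cost is about 1 to 2 power points or less when 1-2% of subjects are affected, about 2 points at 5% and about 5 points at 10%. These sizes rest on assumed closure shares and times, on closures that hit both arms alike, on the plan's exponential 45% v 55%, and on an unstratified test where the plan stratifies.

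The bias is conservative when both arms are affected equally, and it cannot then produce a false claim of superiority. The 90% figure needs no correction. Section 18.5 is not at fault; the sentence to change is the unconditional rule in section 17 and its subsections. For a temporary suspension it is unclear whether the rule applies at all, because 17.3 does not require the discontinuation to be permanent while 6.4 encourages subjects to restart.

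**What to change.** Add to 17.3, and to the matching sentence in 17 and 17.1:

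> Subjects whose treatment ends only because their site or the trial is permanently closed for administrative reasons unrelated to the safety or efficacy of either trial product are right-censored at the last HbA1c assessment before closure. All other withdrawals and discontinuations, including stops of one arm or stops for product safety, remain events.

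In addition:
- Apply the same rule in both interval-censored sensitivity analyses.
- Report the version that counts all discontinuations as events as a sensitivity analysis.
- Add administrative closure of the site or trial as a recorded reason for discontinuation; 8.1.8 already requires a reason in the eCRF.
- Do not apply the rule to temporary suspensions after which treatment resumes.
- Leave the responder analyses in 17.4.1.1 on non-response imputation unless a missing-data method is specified for these subjects.

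The cost is one sentence, one reason code and one further sensitivity analysis. Somewhat fewer events are counted (490 instead of 525 with 5% closed), but power was higher with censoring than with the rule as written at each share tabulated. The change should be made before any closure occurs, because a later change in an open-label trial could look data-driven.

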23.1 Communication of results

Novo Nordisk commits to communicating, and otherwise making available for public disclosure, results of trials regardless of outcome. Public disclosure includes publication of a paper in a scientific journal, abstract submission with a poster or oral presentation at a scientific meeting, or disclosure by other means.

The results of this trial will be subject to public disclosure on external web sites according to international and national regulations, as reflected in the Novo Nordisk Code of Conduct for Clinical Trial Disclosure.¹²

Novo Nordisk reserves the right to defer the release of data until specified milestones are reached, for example when the clinical trial report is available. This includes the right not to release the results of interim analyses, because the release of such information may influence the results of the entire trial.

At the end of the trial, one or more scientific publications may be prepared collaboratively by the investigator(s) and Novo Nordisk. Novo Nordisk reserves the right to postpone publication and/or communication for up to 60 days to protect intellectual property.

In all cases the trial results will be reported in an objective, accurate, balanced and complete manner, with a discussion of the strengths and limitations. All authors will be given the relevant statistical tables, figures, and reports needed to evaluate the planned publication. In the event of any disagreement on the content of any publication, both the investigators' and Novo Nordisk opinions will be fairly and sufficiently represented in the publication.

Where required by the journal, the investigator from each trial site will be named in an acknowledgement or in the supplementary material, as specified by the journal.

Novo Nordisk maintains the right to be informed of plans by any investigator to publish and to review any scientific paper, presentation, communication or other information concerning the investigation described in this protocol. Any such communication must be submitted in writing to Novo Nordisk before submission for comments. Comments will be given within four weeks from receipt of the planned communication.

23.1.1 Authorship

Authorship of publications should be in accordance with the Uniform Requirements of the International Committee of Medical Journal Editors³⁴ (sometimes referred to as the Vancouver Criteria).

23.1.2 Site-specific publications by investigators

For a multi-centre clinical trial, analyses based on single-site data usually have significant statistical limitations and frequently do not provide meaningful information for healthcare professionals or subjects, and therefore may not be supported by Novo Nordisk. It is a Novo Nordisk policy that such individual reports do not precede the primary manuscript and should always reference the primary manuscript of the trial.

Novo Nordisk reserves the right to prior review of such publications. Further to allow for the primary manuscript to be published as the first, Novo Nordisk asks for deferment of publication of individual site results until the primary manuscript is accepted for publication. As Novo Nordisk wants to live up to the industry publication policy, submission of a primary publication will take place no later than 18 months after trial completion.

23.2 Investigator access to data and review of results

As owner of the trial database, Novo Nordisk has the discretion to determine who will have access to the database.

Individual investigators will have their own research subjects' data.

24 Retention of clinical trial documentation

Subject's medical records must be kept for the maximum period permitted by the hospital, institution or private practice.

The investigator must agree to archive the documentation (this includes both electronic and paper-based records) pertaining to the trial in an archive after completion or discontinuation of the trial if not otherwise notified. The investigator should not destroy any documents without prior permission from Novo Nordisk. If the investigator cannot archive the documents at the trial site, Novo Nordisk can refer the investigator to an independent archive provider that has a system in place to allow only the investigator to access the files.

The investigator must be able to access his/her trial documents without involving Novo Nordisk in any way. Site-specific CRFs and other subject data (in an electronic readable format or as paper copies or prints) will be provided to the investigator before access is revoked to the systems and/or electronic devices supplied by Novo Nordisk. These data must be retained by the trial site. If the provided data (e.g. the CD-ROM) is not readable during the entire storage period, the investigator can request a new copy. A copy of all data will be stored by Novo Nordisk.

Novo Nordisk will maintain Novo Nordisk documentation pertaining to the trial for as long as the product is on the market plus 20 years.

The files from the trial site/institution must be retained for 15 years after the completion of the trial, or longer if required by local regulations or Novo Nordisk. In any case trial files cannot be destroyed until the trial site/institution is notified by Novo Nordisk. The deletion process must ensure confidentiality of data and must be done in accordance with local regulatory requirements.

25 Institutional Review Boards/Independent Ethics Committees and regulatory authorities

IRB/IEC:

Written approval or favourable opinion must be obtained from IRB/IEC prior to commencement of the trial.

During the trial, the investigator or Novo Nordisk, as applicable, must promptly report the following to the IRB/IEC, in accordance with local requirements: updates to Investigator's Brochure, unexpected SAEs where a causal relationship cannot be ruled out, protocol amendments according to local requirements, deviations to the protocol implemented to eliminate immediate hazards to the subjects, new information that may affect adversely the safety of the subjects or the conduct of the trial (including new benefit-risk analysis in case it will have an impact on the planned follow-up of the subjects), annually written summaries of the trial status, and other documents as required by the local IRB/IEC.

The investigator must ensure submission of the CTR synopsis to the IRB/IEC.

Protocol amendments must not be implemented before approval or favourable opinion according to local regulations, unless necessary to eliminate immediate hazards to the subjects.

The investigator must maintain an accurate and complete record of all submissions made to the IRB/IEC. The records must be filed in the investigator trial master file and copies must be sent to Novo Nordisk.

Regulatory Authorities:

Regulatory authorities will receive the clinical trial application, protocol amendments, reports on SAEs, and the CTR according to national requirements.

26 Indemnity statement

Novo Nordisk carries product liability for its products, and liability as assumed under the special laws, acts and/or guidelines for conducting clinical trials in any country, unless others have shown negligence.

Novo Nordisk assumes no liability in the event of negligence, or any other liability of the sites or investigators conducting the trial, or by persons for whom the said site or investigator are responsible.

Novo Nordisk accepts liability in accordance with:

Russia: Federal Law of 12 April 2010 No. 61-FZ "On Medicinal Drugs' Circulation.

Poland: Novo Nordisk carries liability for the Study exclusively in the scope defined by the applicable laws and in particular by the Civil Code and the Pharmaceutical Law dated 6 September 2001 (uniform version Journal of Laws of 2008 No. 45 item 271 with amendments). In order to support potential claims for liability attributable to the Study, Novo Nordisk and Investigator are covered by the Insurance Policy issued according to applicable Polish law.

